Appendix 10.4: General Medical Laboratory Screen Tests Information Table

Analysis	Test	Methodology	Specimen Minimum Volume	Specimen Transport Temperature	Reference Values		
					Gender	Age	Reference Ranges
Heamatology							
	Haematocrit	GENS	7 ml	Ambient storage/ ambient transport	F	18-120	0.35 - 0.47
					M	18-120	0.37 - 0.51
					B	0-0	0.28 - 0.42
					B	1-7	0.32 - 0.42
					B	8-17	0.33 - 0.44
	Haemoglobin (g/L)	GENS			F	18-120	115 - 165 AL 50
					M	18-120	130 - 174 AL 50
	Red Blood Cell Count (X10E12/L)	GENS			F	18-120	4.00 - 5.50
					M	18-120	4.50 - 6.00
					B	0-0	3.30 - 5.30
					B	1-7	3.70 - 5.30
					F	8-17	3.80 - 5.10
					M	8-17	3.80 - 5.60
	Mean Cell Volume				Calculation		
	MCHC				Calculation		
	White Blood Cell Count (X10E9/L)	GENS			B	18-120	3.6 - 11.0
	Differential Blood Count	GENS			Calculation		
	Absolute Platelet Count (X10E9/L)	GENS			B	18-120	150 - 400
BioChemistry	Total Bilirubin (umol/L)	BMC Hitachi 911	9.5 ml	Ambient storage / ambient transport	B	13-120	0.0 - 22.1
					B	1-12	0.0 - 25.6

Analysis	Test	Methodology	Specimen Minimum Volume	Specimen Transport Temperature	Reference Values		
					Gender	Age	Reference Ranges
	Creatinine (umol/L)	BMC Hitachi 911			M	10-49	0 - 114 AH 650
					F	10-120	0 - 96 AH 650
					M	50-120	0 - 123 AH 650
					B	9-9	0 - 90 AH 650
					B	8-8	0 - 80 AH 650
					B	7-7	0 - 70 AH 650
					B	6-6	0 - 60 AH 650
					B	5-5	0 - 50 AH 650
					B	0-4	0 - 40 AH 650
	Blood Urea Nitrogen (mmol/L)	BMC Hitachi 911			B	14-120	1.7 - 8.3 AH 35.0
					B	1-13	1.7 - 7.0 AH 35.0
	TSH (serum) (mIU/L)	Abbott AXSYM MEIA			B	0-120	0.30 - 5.50
	ft4 (serum) (ng/dl)	Abbott AXSYM MEIA			B	1-9	6.0-12.5
					B	10-17	5.0-11.0
					F	18-120	5.0-12.5
					M	24-120	5.0-12.5
Urinalysis (Routine & Microscopic)	Blood	Ames Multistix 10SG	10 ml	Ambient storage / ambient transport	Calculation		
	Leukocytes				Calculation		
	Protein				Calculation		
	pH				Calculation		
	Nitrates				Calculation		
	Glucose				Calculation		
	Possible Microscopic Analysis				Calculation		
Cotinine (plasma) (ng/ml)		Gas Chromotography	5 ml	Ambient storage / ambient transport	B	0-120	20-700 in smokers

Legend: F- Female M - Male B - Both AH - Alert Hi AL - Alert Lo

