3.2.2.1.2 Urinalysis

Urine removes toxins and excess liquid from the body and can therefore contain important clues regarding a person's general health and exposure to contaminants.

Urinalysis can be used to detect certain types of disease, particularly in the case of metabolic disorders and kidney disease. Urinalysis will include macroscopic examination (test strips) for: blood (Hb, erythrocytes), leukocytes, protein, pH, nitrite, and glucose for all the residents tested. Microscopic examination of urine sediment will be performed if there is a positive macroscopic result for blood, leukocytes protein (greater than trace), or if the glucose concentration is greater than 55 millimicromolars (nmol/l).

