3.2.2.5 Validation

The individual medical tests described above have been included both for their utility in measuring general health and health conditions associated with exposure to the CoCs, as well as for purposes of validation. That is, specific medical tests also can be used as objective measures to validate reported medical health information from the health

questionnaire that is subjective in nature (Moffat et al., 2000; Smith- Sivertsen et al., 2000).

Medical tests that will serve as validators in this study include:

- Bilirubin test: validates the jaundice question in the questionnaire,
- Plasma cotinine test: validates recent smoking history question in the questionnaire,
- Serum TSH and fT4 test: validates thyroid condition questions in untreated individuals,
- ECG test: validates history of heart attack question in the health questionnaire,
- CO breath test: validates recent smoking history question in the health questionnaire,
- FEV1/FVC/PEFR tests: help to validate chronic bronchitis, emphysema, chronic obstructive pulmonary disease, asthma and other respiratory questions from the health questionnaire, and
- Skin patch tests: validates contact dermatitis question from the health questionnaire.

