6.2.2.1 General medical laboratory screen tests

The general medical laboratory screen tests will include a number of measures that are based on the collection of blood and urine. Blood-based measures will include both haematology measures and biochemistry measures. Haematology outcome measures will provide concentrations, counts and volumes for blood-based parameters. Biochemistry outcome measures will include concentrations of total bilirubin, creatinine, blood urea nitrogen, cotinine, TSH and fT4. Urinalysis outcome measures will include presence of blood, leukocytes, protein, and glucose as well as nitrate concentrations and pH levels.

These measures will be expressed both in terms of mean values and within reference range frequency counts. Where the distribution of measured values are found to be non-normal, median values will be presented rather than means.

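### Appendix 10.4 as printed cannot support the planned in-range counts: age bands are missing for four tests, the free T4 unit and range probably do not match, and the urine glucose trigger in Section 3.2.2.1.2 is very probably misprinted

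*Protocol*

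**What the plan says.** **Use of the ranges.** Protocol Section 6.2.2.1 names free T4 among the biochemistry outcomes and says the laboratory measures will be "expressed both in terms of mean values and within reference range frequency counts". Section 6.3.4 says the ranges supplied by the laboratory will describe these outcomes. It points to the laboratory appendix as 11.4, which this version numbers 10.4. Section 3.2.2.5 gives free T4 a second job: "Serum TSH and fT4 test: validates thyroid condition questions in untreated individuals".

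**The free T4 row.** Appendix 10.4 labels it "ft4 (serum) (ng/dl". The printed bands are 6.0-12.5 (both sexes, 1-9), 5.0-11.0 (both sexes, 10-17), 5.0-12.5 (women, 18-120) and 5.0-12.5 (men, 24-120).

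**Other rows.** Haemoglobin, white cell count and platelets have bands for ages 18-120 only. Haematocrit and red cell count, in the same block, also print bands for 8-17. Section 4.1.1.1.1 admits residents aged 12 or older.

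**Urine glucose.** Section 3.2.2.1.2 says "Urinalysis will include macroscopic examination (test strips" for blood, leukocytes, protein, pH, nitrite and glucose. Sediment microscopy follows a positive result for blood, leukocytes or protein, "or if the glucose concentration is greater than 55 millimicromolars (nmol/l". Appendix 10.4 gives the method as "Ames Multistix 10SG" and shows no glucose unit or numerical limit. In reporting, "Urinalysis outcome measures will include presence of blood, leukocytes, protein, and glucose".

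**The concern.** An in-range count needs, for every participant, a result and a limit on the same scale, and a limit that applies to that participant's age and sex. Appendix 10.4 fails the second condition for some eligible participants in four rows, and probably fails the first in the free T4 row.

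Missing bands leave those participants unclassified, or classified by an unstated substitute. For haemoglobin, white cells and platelets this reaches a planned comparison: mock Table 10 sets the proportions outside the normal range in Area 3 against the rest of Port Colborne.

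A unit that does not belong to its range would make the free T4 counts wrong. It would also spoil the free T4 part of the check on self-reported thyroid disease. Section 1.2.1.3 cites a possible link between prolonged cobalt exposure and altered thyroid function, so the analyte is not incidental. Section 3.4 foresees that values of concern will be communicated to the subject and local physician, so classification also matters beyond the tables.

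The glucose limit is a lesser matter. It decides which urines go on to microscopy.

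**Working it through.** **1. Age coverage.** Eligible ages run from 12 upward (Section 4.1.1.1.1). Each Appendix 10.4 row with numerical bands was checked for every age from 12 to 120.

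| Row | Bands that bear on ages 12+ | Ages with no band |
|---|---|---|
| Free T4, men | 10-17, 24-120 | 18-23 |
| Free T4, women | 10-17, 18-120 | none |
| Haemoglobin | 18-120 | 12-17 |
| White cell count | 18-120 | 12-17 |
| Platelets | 18-120 | 12-17 |
| Haematocrit, red cell count | 8-17, 18-120 | none |
| Bilirubin, creatinine, urea nitrogen, TSH | complete | none |

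Each gap spans six single years of age. The protocol gives no count of residents at those ages, so the number of participants affected cannot be stated.

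**2. Free T4 unit.** The printed lower limit is 5.0 ng/dl for everyone aged 10 or over who has a band. The protocol gives no usual free T4 level, so one must be assumed. Take any value from 0.5 to 3 ng/dl.

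- At 0.5 ng/dl, the limit is 5.0 / 0.5 = 10 times the value.
- At 3 ng/dl, the limit is 5.0 / 3 = 1.7 times the value.

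Every value in the assumed span is below the limit. The result does not depend on the exact span: any usual level under 5.0 ng/dl gives the same answer. If results are reported in ng/dl, nearly all would therefore be counted as low.

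**3. Glucose trigger.** Taking the molar mass of glucose as 180.16 g/mol:

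- 55 × 10⁻⁹ mol/l × 180.16 g/mol = 9.9 × 10⁻⁶ g/l = 9.9 µg/l = 0.00099 mg/dl.
- The same number in µmol/l would be 0.99 mg/dl, and in mmol/l 991 mg/dl. Each prefix step changes the limit a thousandfold.

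If ordinary urine glucose is assumed to lie between 0.01 and 1 mmol/l (not in the protocol), the ratio to the printed limit is:

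- 0.01 × 10⁻³ / 55 × 10⁻⁹ = about 180;
- 1 × 10⁻³ / 55 × 10⁻⁹ = about 18,000.

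On that assumption practically every urine exceeds the limit. A nanomolar cut-off also sits oddly beside a strip test for which protein is graded relative to trace and glucose is reported as present or absent.

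**4. Where each item is used.** Mock Table 10 lists haemoglobin, white cells and platelets, so the 12-17 gaps reach a tabulated comparison. Mock Tables 7 and 10 list TSH but not free T4, so the free T4 problems reach the in-range counts of Section 6.2.2.1 and the validation of Section 3.2.2.5, but not those tables. No mock table reports urinalysis.

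**The case against.** The strongest reply is that the protocol does not contradict itself on the free T4 unit. It prints one unit and one set of limits, and no free T4 value elsewhere conflicts with them. The mismatch appears only once an outside level is assumed. That is correct, and it is why this part is put as probable.

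A reader might go further and infer that almost everyone will be flagged low, that false abnormal results will go out, and that the thyroid validation fails. The protocol does not support this unconditionally:

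- The ranges come from the laboratory, and results arrive electronically in a predetermined format (Section 5.1). If only the printed label is wrong, results and limits still match and participants are sorted correctly.
- The thyroid validation uses TSH together with free T4, and TSH has a complete band for ages 0-120.
- Section 3.4 says values of concern will be put into context in the analysis and in communication. This softens individual misreporting, although it does not repair a count.

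It would also be wrong to read the glucose limit as classifying participants. It is one of four microscopy triggers, beside blood, leukocytes and protein. The spelled-out unit and its symbol agree with each other, and no strip sensitivity is stated, so the prefix error is an inference.

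Finally, a table row could have been lost when the PDF was read. That cannot be excluded, but neighbouring rows with adolescent bands came through cleanly. If the source table does contain the missing bands, part of the point falls away on inspection.

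**Conclusion.** The point holds in three parts of unequal strength.

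- **Missing bands** rest on the protocol alone, subject to the extraction caveat: free T4 for men aged 18-23, and haemoglobin, white cells and platelets for ages 12-17. The last three matter most because mock Table 10 depends on them.
- **Free T4 unit and range** probably do not belong together. This assumes a usual level below 5.0 ng/dl. The consequences, nearly all results counted as low and a faulty free T4 part of the thyroid validation, hold only if ng/dl is also the unit in which results are reported.
- **The glucose trigger** of 0.00099 mg/dl is very probably a prefix error. It bears on who gets microscopy and on no tabulated comparison.

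None of this affects sample size or power. It should still be corrected, because these limits are fixed in the protocol itself and would be applied as they stand.

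**What to change.** Before any result is classified or released, put one query to the central laboratory asking it to:

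1. confirm the free T4 unit and the matching reference interval for its stated method;
2. supply bands covering both sexes at every age from 12 up for each Appendix 10.4 row used for in-range counts, including free T4 for men aged 18-23 and haemoglobin, white cells and platelets at 12-17;
3. confirm the unit of the glucose trigger as the strip reports it.

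Then amend Appendix 10.4 and Section 3.2.2.1.2 so that they agree. Which limits are right is for the laboratory and the sponsor to settle. The cost is one query and edits in two places, with no added tests and no change to the sample.

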6.3.4 Reference Values and Population Normal Data

There are very few questions in the health questionnaire that do not come from standardized questionnaires. In these instances, prevalence data from published literature will be used to assess the data collected in this study.

With respect to laboratory and clinical data, standard reference ranges supplied by the laboratory (see Appendices 11.4 and 11.5) and standard clinical practice guidelines will be used to describe these outcomes.

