Comparison of the Mean Levels of Selected Biological Measures, by Sampling Areas,
CHAP Comprehensive Health Questionnaire, Fall 2002

	Area 3	Areas 1, 2, 4, 5	Total for Port Colborne	p-value [†]
	Mean (s.d)*	Mean (s.d)	Mean (s.d)*	
Haemoglobin				
White Blood Cell Count				
Red Blood Cell Count				
Haematocrit				
Mean Cell Volume of Red Cells				
Mean Hemoglobin Concentration of Red Cells				
Platelet Count				
Red Cell Distribution Width				
Mean Platelet Volume				
Differential Leukocyte Count				
Bilirubin				
Creatinine				
Plasma Cotinine				
Plasma Screen for Concentration of TSH				
Blood Urea Nitrogen				

[†] p-value is based on an ANOVA for comparing the means between Area 3, and Areas 1, 2, 4, and 5; after adjusting for difference in the age and sex distribution of the two populations.

* s.d. = standard deviation

Table 8.
Comparison of the Non-Specimen Tests Among Participants, by Sampling Areas,
CHAP Comprehensive Health Questionnaire, Fall 2002

	Area 3	Areas 1, 2, 4, 5	Total for Port Colborne	p-value [†]
	Mean (s.d) [*]	Mean (s.d)	Mean (s.d.)	
Calculated BMI				
Electrocardiogram	---	---	---	---
Blood Pressure				
Carbon Monoxide Breath Test				
Forced Expiratory Volume in 1 second				
Forced Vital Capacity				
Peak Expiratory Flow Rate				
Dermatology Patch: Nickel Sulfate				
Dermatology Patch: Cobalt Dichloride				

[†] p-value is based on an ANOVA for comparing the means between Area 3, and Areas 1, 2, 4, and 5; after adjusting for difference in the age and sex distribution of the two populations.

^{*} s.d. = standard deviation

Table 9.
Comparison of the Selected Measures of Chemicals Among Participants, by Sampling Areas, CHAP Comprehensive Health Questionnaire, Fall 2002

	Area 3	Areas 1, 2, 4, 5	Total for Port Colborne	p-value [†]
Chemical	Mean (s.d) [*]	Mean (s.d)	Mean (s.d)	
Nickel (Urine)				
Copper (Urine)				
Cobalt (Urine)				
Arsenic (Urine)				
Mercury (Urine)				
Lead (Blood)				

[†] p-value is based on an ANOVA for comparing the means between Area 3, and Areas 1, 2, 4, and 5; after adjusting for difference in the age and sex distribution of the two populations.

^{*} s.d. = standard deviation

Table 10.
Comparison of the Proportion of Tests Outside Normal Range for Selected Biological Measures,
by Sampling Areas,
CHAP Comprehensive Health Questionnaire, Fall 2002

	Area 3	Areas 1, 2, 4, 5	Total for Port Colborne	p-value [†]
Proportion Outside Normal Range				
Haemoglobin (normal range)				

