White Blood Cell Count (normal range)				
Red Blood Cell Count (normal range)				
Haematocrit (normal range)				
Mean Cell Volume of Red Cells (normal range)				
Mean Hemoglobin Concentration of Red Cells (normal range)				
Platelet Count (normal range)				
Red Cell Distribution Width (normal range)				
Mean Platelet Volume (normal range)				
Differential Leukocyte Count (normal range)				
Bilirubin (normal range)				
Creatinine (normal range)				
Plasma Cotinine (normal range)				
Plasma Screen for Concentration of TSH (normal range)				
Blood Urea Nitrogen (normal range)				

[†] p-value is based on logistic regression analysis controlling for differences in the age and sex distribution of the two sampling areas

Table 11.
Comparison of the Proportion of Non-specimen Tests Outside Normal Range, by Sampling Areas, CHAP Comprehensive Health Questionnaire, Fall 2002

	Area 3	Areas 1, 2, 4, 5	Total for Port Colborne	p-value [†]
Proportion Outside Normal Range				
Calculated BMI (average range)				
Electrocardiogram [‡]				
Blood Pressure (normal range)				
Carbon Monoxide Breath Test (normal range)				
Forced Expiratory Volume in 1 second (normal range)				
Forced Vital Capacity (normal range)				
Peak Expiratory Flow Rate (normal range)				
Dermatology Patch: Nickel Sulfate (normal range)				
Dermatology Patch: Cobalt Dichloride (normal range)				

[†] p-value is based on logistic regression analysis controlling for differences in the age and sex distribution of the two sampling areas

[‡] proportion with abnormal electrocardiogram

Table 12.
Comparison of the Proportion of Chemical Measures Outside Normal Range, by Sampling Areas, CHAP Comprehensive Health Questionnaire, Fall 2002

	Area 3	Areas 1, 2, 4, 5	Total for Port Colborne	p-value [†]
	Proportion Outside Normal Range			
Nickel (Urine) (normal range)				
Copper (Urine) (normal range)				
Cobalt (Urine) (normal range)				
Arsenic (Urine) (normal range)				
Mercury (Urine) (normal range)				
Lead (Blood) (normal range)				

[†] p-value is based on logistic regression analysis controlling for differences in the age and sex distribution of the two sampling areas.

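### Plasma cotinine has only a smokers' reference range, so its row in mock Table 10 is either inverted or undefined for non-smokers

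*Protocol*

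**What the plan says.** - Appendix 10.4 has a single entry for plasma cotinine (ng/ml), for both sexes and ages 0-120: "20-700 in smokers". No range for non-smokers appears anywhere in the protocol.
- Section 6.2.2.1 makes cotinine an outcome: "Biochemistry outcome measures will include concentrations of total bilirubin, creatinine, blood urea nitrogen, cotinine, TSH and fT4". It says the general laboratory measures will be summarised by means (or medians) and by "within reference range frequency counts".
- Section 6.3.4 says laboratory and clinical outcomes will be described using "standard reference ranges supplied by the laboratory", together with clinical practice guidelines. It cites Appendices 11.4 and 11.5, which are printed as 10.4 and 10.5.
- Mock Table 10 in section 6.5.1 is titled "Comparison of the Proportion of Tests Outside Normal Range for Selected Biological Measures" and has a plasma cotinine row. Its columns are Area 3, Areas 1, 2, 4 and 5 combined, the total, and a p-value. The footnote reads: "p-value is based on logistic regression analysis controlling for differences in the age and sex distribution of the two sampling areas".
- Sections 3.2.2.5 and 3.3.6 give cotinine's purpose: to separate tobacco-exposed from unexposed people and to check self-reported recent smoking.
- Section 6.2.2.3 handles the companion marker, breath CO, by a smoking-abstinence threshold. It mentions cotinine there only as further validation and gives no cut-off for it.

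**The concern.** For most analytes in Table 10, being inside the laboratory range is the unremarkable result. For cotinine, the only listed range describes people who smoke, and a low value means no tobacco exposure. A rule that flags values outside that range therefore flags the unexposed. An area with more smokers could appear to have fewer abnormal results, in the table meant to compare the higher-exposure area with the rest of the city. The Table 10 model adjusts for age and sex only, so nothing in it would correct or reveal this.

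**Working it through.** The protocol states no expected cotinine result, so there is no figure to reproduce. The check applies the rule as written and compares it with a rule based on exposure.

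**Inputs**
- Range 20-700 ng/ml (Appendix 10.4).
- Smoking rate of 30% elsewhere in the city. Section 6.1 uses 30% only as a hypothetical to explain sampling variation, so it is an assumption here; 20% is also shown.
- Smoking rates in Area 3 of 25% to 40%: assumptions, since the documents give none.
- 500 participants per group (the figure used in section 6.1.1).

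**Reading A: 20-700 applied to everyone.** Let s be the share of participants inside 20-700. Suppose first that every smoker is inside and every non-smoker is below 20, so that s is the smoking rate.
- Proportion outside the range = 1 − s. At s = 0.30 this is 70% of participants.
- Proportion at or above 20 = s (values above 700 ignored). The value 20 serves only to illustrate the arithmetic.
- The odds of being outside are (1 − s)/s and the odds of exposure are s/(1 − s), so one area odds ratio is always the reciprocal of the other.

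Worked case, 40% in Area 3 and 30% elsewhere:
- Outside range: (0.60/0.40)/(0.70/0.30) = 1.500/2.333 = 0.64.
- Exposed: (0.40/0.60)/(0.30/0.70) = 0.667/0.429 = 1.56.

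| Assumed smoking, Area 3 vs rest | Outside range | OR as written | OR for exposure |
|---|---|---|---|
| 30% vs 30% | 70% vs 70% | 1.00 | 1.00 |
| 35% vs 30% | 65% vs 70% | 0.80 | 1.26 |
| 40% vs 30% | 60% vs 70% | 0.64 | 1.56 |
| 40% vs 20% | 60% vs 80% | 0.375 | 2.67 |
| 25% vs 30% | 75% vs 70% | 1.29 | 0.78 |

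**Imperfect classification.** Suppose 95% of smokers fall inside the range and 3% of non-smokers reach 20. For 40% vs 30% smoking:
- Inside, Area 3: 0.40 × 0.95 + 0.60 × 0.03 = 0.398. Inside, rest: 0.30 × 0.95 + 0.70 × 0.03 = 0.306.
- OR outside: (0.602/0.398)/(0.694/0.306) = 0.67, against 1.50 for exposure. The inversion remains.

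**Chance of significance.** With 500 per group, two-sided alpha 0.05 and perfect classification, an unadjusted two-proportion comparison has power of about 0.91 for 40% vs 30% and 0.39 for 35% vs 30%. Power is the same whichever way the outcome is coded, so a significant result in the wrong direction is plausible if smoking differs by 10 points.

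**Reading B: the range holds for smokers only.** Non-smokers then have no normal range. Table 10 neither restricts the row to smokers nor includes a smoking term, so the row cannot be completed for non-smokers.

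**The case against.** The best counter-argument is that the entry is qualified. Read as printed, it does not classify a non-smoker at all, so the row is incomplete rather than inverted. That is fair, and it is why inversion is given here as one of two readings. It does not rescue the row, because Reading B leaves most participants unclassified under the 30% assumption.

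A second argument is that the normal-range label in the mock tables is a generic placeholder. Table 11 attaches it to patch tests that are scored only positive or negative. Several Table 10 rows have no numeric range in Appendix 10.4: MCV, MCHC and the differential count are entered as calculations, and RDW and MPV are not listed. This stands, and it shows that Table 10 cannot be filled mechanically from the appendix. Cotinine differs in that a numeric range is printed there and could be picked up.

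Third, section 6.3.4 also admits clinical practice guidelines, and an unseen analysis plan might fix a cut-off. The protocol names no guideline for cotinine, though, and what it does state conflicts with the marker's purpose in sections 3.2.2.5 and 3.3.6.

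Fourth, the effect is contained, and this stands in full. Table 4 reports smoking status by area, Table 7 compares cotinine levels without any reference range, and the risk models in section 6.4 adjust for smoking habits rather than for a Table 10 flag.

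A reader might infer that the area comparison will point the wrong way, or that control of smoking as a confounder is compromised. The documents support neither. The first needs both Reading A and a smoking difference between areas, for which no rates are given. The second fails because neither the adjustment nor the validation passes through Table 10.

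**Conclusion.** The point holds in a limited form. As specified, the cotinine row of Table 10 has no sensible interpretation: it is inverted if the smokers' range is applied to everyone, and undefined for non-smokers if the qualifier is respected. Under the first reading the odds ratio is the exact reciprocal of the exposure odds ratio when everyone is correctly classified, and close to it otherwise. The examples run from 1.00 with equal smoking to 0.375 in place of 2.67 at 40% vs 20%. All smoking rates behind these figures are assumptions. Even with equal rates, a figure of about 70% outside normal, at 30% smoking, would misdescribe the community. This is one secondary table row, worth correcting because the correction is simple.

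**What to change.** Remove plasma cotinine from the outside-normal-range analysis in Table 10. Report instead the proportion at or above one tobacco-exposure cut-off, stated before the data are seen and confirmed with the laboratory. This parallels the breath CO threshold in section 6.2.2.3. The lower end of the smokers' range should not be adopted as that cut-off without confirmation, since the documents do not present it as one. Add the agreement between the cotinine classification and self-reported smoking, which serves the validation purpose in section 3.2.2.5.

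State in section 6.2.2.1 that reference-range counts do not apply to cotinine, and mark the Appendix 10.4 entry as not for use in Table 10. Table 7 needs no new rule, because section 6.2.2.1 already calls for medians where values are non-normal.

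The cost is one table row, a line in section 6.2.2.1, a note in the appendix and one query to the laboratory. No extra data or participants are needed.
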